14.0 REPORTING AND EXCLUSIONS

14.1 Evaluation of toxicity:

Patients will be evaluable for toxicity related to the targeted therapy given in the first stage and in the second stage.

14.2 Evaluation of response:

All patients who are registered and assigned to treatment will be assessed for response. All patients who met the eligibility criteria (with the possible exception of those who received no study medication) should be included in the main analysis of the response rate. Patients with an incorrect treatment schedule or drug administration does not result in exclusion from the analysis of the response rate. Precise definitions for categories 4-8 will be protocol specific.

All conclusions should be based on all eligible patients. Sub-analyses may then be performed on the basis of a subset of patients, excluding those for whom major protocol deviations have been identified (e.g., early death due to other reasons, early discontinuation of treatment, major protocol violations, etc.). However, these sub-analyses may not serve as the basis for drawing conclusions concerning treatment efficacy, and the reasons for excluding patients from the analysis should be clearly reported. Data analysis will be performed using SAS or S-Plus, as appropriate. Patients who die of unrelated cause during therapy or are lost to follow-up shall be censored.

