2.3 Rationale

In the past few years, considerable progress has been made in the management of patients with metastatic renal cell carcinoma (RCC). There are now six (five in the first-line setting) FDA-approved treatments for metastatic RCC, however most patients experience disease progression within a year or less. The vast majority of metastatic RCC patients who were enrolled on phase 3 trials with anti-VEGF therapies, sorafenib, sunitinib, pazopanib and bevacizumab plus interferon alfa had good- or intermediate-risk disease. Temsirolimus is the standard of care for the treatment of patients with advanced poor-risk RCC, based on results from a phase 3 trial comparing single-agent temsirolimus versus single-agent interferon alfa versus the combination of temsirolimus and interferon alfa. The response rate of temsirolimus in this study was 8.4 %, and the median PFS and median OS were 3.8 months and 10.9 months, respectively. There is no data on the efficacy of multityrosine kinase inhibitors (TKI) in this disease state. Therefore, it is important to investigate agents with the oral convenience and tolerability of TKIs, such as pazopanib, in advanced poor-risk RCC.

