3.2.3 Clinical Studies

A phase 3, multi-center, three-arm, randomized, open-label study was conducted in previously untreated patients with advanced renal cell carcinoma (clear cell and non-clear cell histologies). The objectives were to compare Overall Survival (OS), Progression-Free Survival (PFS), Objective Response Rate (ORR), and safety in patients receiving IFN- α to those receiving temsirolimus and temsirolimus plus IFN- α . Patients in this study had 3 or more of 6 pre-selected prognostic risk factors (less than one year from time of initial RCC diagnosis to randomization, Karnofsky performance status of 60 or 70, hemoglobin less than the lower limit of normal, corrected calcium of greater than 10 mg/dL, lactate dehydrogenase > 1.5 times the upper limit of normal, more than one metastatic organ site). Patients were stratified for prior nephrectomy status within three geographic regions and were randomly assigned (1:1:1) to receive IFN- α alone (n=207), temsirolimus alone (25 mg weekly; n=209), or the combination arm (n=210).

The ITT population for this interim analysis included 626 patients. Demographics were comparable between the three treatment arms with regard to age, gender, and race. The mean age of all groups was 59 years (range 23-86). Sixty-nine percent were male and 31% were female. The racial distribution for all groups was 91% White, 4% Black, 2% Asian, and 3% other. Sixty-seven percent of patients had a history of prior nephrectomy.

The median duration of treatment in the temsirolimus arm was 17 weeks (range 1-126 weeks). The median duration of treatment on the IFN arm was 8 weeks (range 1-124 weeks).

There was a statistically significant improvement in OS (time from randomization to death) in the temsirolimus 25 mg arm compared to IFN- α . The combination of temsirolimus 15 mg and IFN- α did not result in a significant increase in overall survival when compared with IFN- α alone.

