5.2 Administration

After registration on the protocol, patients will be randomized to receive either pazopanib or temsirolimus treatment. Following randomization patients will begin treatment with the first assigned agent. At progression, if they have not suffered an adverse event that would preclude them from continuing with systemic therapy, after the applicable washout period, will begin treatment with the remaining treatment agent at the discretion of the physician.

Pazopanib will be taken at 800 mg PO daily without food (at least 1 hour before or 2 hours after a meal) until PD or prohibitive toxicity or withdrawal of consent. Tablets will not be crushed due to the potential for increased rate of absorption which may affect systemic exposure. If a dose is missed, it should not be taken if it is less than 12 hours until the next dose. Patients will complete a pill diary for pazopanib to document compliance.

Temsirolimus will be given at 25 mg IV infused over 30-60 minutes every week until PD or prohibitive toxicity or withdrawal of consent. Patients will receive prophylactic intravenous diphenhydramine 25 to 50 mg (or similar antihistamine) approximately 30 minutes before the start of each dose of temsirolimus.

A cycle consists of 4 weeks of therapy. Pazopanib will be self-administered at home and in the outpatient setting for patients who receive temsirolimus.

All patients will have a washout period of 2 weeks from the day of progressive disease tumor assessment before they start 2nd-line therapy.

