13.0 STATISTICAL CONSIDERATIONS

This is a randomized, two-arm, parallel group, phase II trial enrolling advanced, poor-risk, clear-cell RCC. Patients will be fairly randomized to either temsirolimus (control arm) or pazopanib (experimental arm).

The maximum sample size to be accrued is 90 patients (45 in each treatment arm). The primary measure of efficacy and primary endpoint is progression free survival (PFS). PFS will be monitored on an interim basis and we will use stopping rules for futility to serve as guidelines for early termination. The stopping rules are ad-hoc in nature but are selected in a manner such that the overall type 1 error is controlled at a one-sided 10% with 80% power.

Descriptive and inferential statistics will be used to summarize treatment effects. The mean, standard deviation, median, 25% percentile, 75% percentile, minimum, and maximum will be reported for continuous variables. For discrete variables, descriptive analyses will be based on the distribution of discrete outcomes and will be reported as percentages and patient counts. Time to event endpoints will be descriptively summarized by Kaplan-Meier curves. Point and interval estimates of treatment effect will be based on maximum likelihood methods. For binomially distributed variables, we will report differences in proportions between treatment groups and the 95% confidence interval associated with those differences. We will estimate treatment effects for time to event variables via hazard ratios using Wald scores from Cox proportional hazard regression models. Unless stated otherwise, all statistical tests will be assessed using a two-sided $\alpha = 0.05$ alpha significance level and confidence intervals will be constructed using two-sided 95% and will be based on the normal approximation. Although multiple secondary endpoints will be evaluated we will make no adjustment for multiplicities associated with these multiple tests.

Estimation of Sample Size

The clinical hypothesis we are assessing in this trial is whether patients receiving the experimental therapy have a lower hazard of progression or death relative to patients receiving the control therapy. The statistical hypothesis is stated as:

$$H_0: \log(HR)=0$$

$$H_A: \log(HR)<0$$

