Where HR is the hazard ratio (experimental:control). For sample size calculation purposes we assume that the median PFS in the temsirolimus arm is 60% that of the pazopanib arm (3.8 months versus 6.1 months). The sample size estimate is based on a one-sided log-rank test with type one error equal to 0.10 and power of 0.80.

We will conduct an interim analysis for futility after 42 events have been observed. If the p-value used to assess futility at the interim analysis is greater than 0.4798 we will stop the trial early for futility.

Secondary Objectives

Overall survival: Overall survival is calculated from day of therapy initiation to the date of death. Patients who are lost to follow-up will be censored at date of last contact.

We will use the Kaplan-Meier estimator to estimate the OS for each group of patients (control, experimental), and the log-rank statistic will be used to test for treatment differences. We will also use the Cox proportional hazards regression model to estimate the hazard ratio (experimental:control) for OS with a 95% confidence interval.

We will also assess the response rate and report 95% confidence intervals.

Additional analyses:

Demographics

For each treatment group (control, experimental), summary statistics will be provided for age, weight, baseline disease status and prior treatments.

Toxicities

Toxicities and side effects that will be evaluated include, but are not limited to infections, renal toxicity, hepatic toxicity, and pulmonary toxicity. Methods of assessment will include monitoring blood counts, and performing laboratory tests as indicated by clinical signs and symptoms. Evidence of toxicities or adverse events will be recorded at all clinic visits. All observed toxicities and side effects will be graded (NCI CTC-AE v. 4.0) for all patients and the degree of association of each with pazopanib or temsirolimus assessed. The incidence and severity of toxicities will be compared between the two treatment arms with Fisher's exact test.

Stratification Factors

The Pocock-Simon Minimization Method will be used to randomize patients according to the following stratification factors:

- Prior nephrectomy status (yes or no)
- Prior cytokine/vaccine therapy (yes or no)

The randomization program based on this method will be developed in the Department of Biostatistics and Applied Mathematics, and the program will be available via an intranet web site of MD Anderson Cancer Center.

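### Section 14.2 rests conclusions on eligible rather than all randomised patients, OS is timed from first treatment, and PFS has neither a stated start date nor its own analysis set

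*Combined protocol and SAP*

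**What the plan says.** Section 14.2 (Evaluation of response) describes three sets of patients:

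- It opens by saying that everyone registered and assigned to treatment will be assessed for response.
- It then narrows the main response-rate analysis: "All patients who met the eligibility criteria (with the possible exception of those who received no study medication) should be included". It gives no rule for when that exception is used.
- Its second paragraph is broader in wording but names only the eligible: "All conclusions should be based on all eligible patients".

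The same paragraph says that sub-analyses leaving out, for example, early deaths or early discontinuations may not support efficacy conclusions.

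Section 13.0 names PFS as the primary endpoint. Its hypothesis implies that the event is progression or death, but no section says when the PFS clock starts or which patients enter the log-rank test. For the secondary endpoint, "Overall survival is calculated from day of therapy initiation to the date of death". Treatment comes after allocation: "Following randomization patients will begin treatment with the first assigned agent" (5.2).

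**The concern.** The value of randomisation lies in comparing everyone allocated, from the moment of allocation. Two features of the plan give up part of that.

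First, a patient found ineligible after randomisation falls outside the set that 14.2 names, and for response an untreated patient may or may not be counted. A daily tablet is compared with a weekly infusion, so patients and investigators know the arm. An exclusion that has not been settled in advance could then be settled with the arm in view.

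Second, an OS clock that starts at first treatment removes a never-treated patient by definition and ignores any death between randomisation and first dose. PFS could be handled the same way or from randomisation, because the text does not choose. The primary result should not depend on a choice made at analysis.

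**Working it through.** **Inputs.** From 13.0: at most 90 patients (45 per arm); median PFS 3.8 v 6.1 months; one-sided type I error 0.10; power 0.80; futility look at 42 events, stopping if p > 0.4798 (taken here as one-sided). From 2.3, for temsirolimus: "the median PFS and median OS were 3.8 months and 10.9 months, respectively", and a response rate of 8.4%. Assumed: exponential times, and the numbers of patients lost.

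**1. The plan's own power.** HR = 3.8/6.1 = 0.623 and ln HR = -0.473. With (1.2816 + 0.8416)^2 = 4.508:

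- Freedman: 4.508 x (1.623/0.377)^2 = 83.5, so 84 events. Half of 84 is the stated interim count of 42.
- Schoenfeld: 4 x 4.508/0.473^2 = 80.5, so 81 events.

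The text does not state a final event count, so 84 is inferred. Power without the look at D events is Phi(sqrt(D/4) x 0.473 - 1.2816), which is 0.8125 at 84. The stated 80% reproduces.

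**2. With the futility look.** The bound is z = 0.0507. Power is the bivariate normal probability with limits sqrt(42/4) x 0.473 - 0.0507 = 1.483 and sqrt(D/4) x 0.473 - 1.2816, and correlation sqrt(42/D).

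| Events D | Second limit | Correlation | Power |
|---|---|---|---|
| 84 | 0.887 | 0.707 | 0.794 |
| 90 | 0.963 | 0.683 | 0.810 |

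One-sided type I error is about 0.094 at 84 events and 0.093 at 90. Even with nobody excluded and an event in every patient, the margin over 80% is one point.

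**3. Random losses from both arms.** From 40,000 simulated trials per row, with no censoring, no interim look and a log-rank test at z = -1.2816 (Monte Carlo SE about 0.2 points for power and 0.15 for type I error):

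| Lost per arm | Power | Type I error |
|---|---|---|
| 0 | 82.3% | 10.3% |
| 2 | 81.0% | 10.2% |
| 4 | 79.6% | 10.4% |

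The power loss is 1.3 and 2.7 points. With the futility look, by the formula in step 2, going from 90 events to 86 or 82 takes power from 0.810 to 0.799 or 0.788. Starting instead from 84 events, leaving out 2%, 5% or 10% of patients gives 0.789, 0.782 or 0.769, against 0.794.

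**4. OS clock.** Assume a one-week (0.230-month) delay to first dose and a median OS of 10.9 months. The chance of death before first dose is 1 - exp(-0.693 x 0.230/10.9) = 1.5%, or about 0.65 of 45 patients.

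**5. Response rate.** A rate of 8.4% in 45 patients is about 4 responders. Counting all 45 gives 4/45 = 8.9%; leaving out two untreated patients gives 4/43 = 9.3%.

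**The case against.** The case for leaving the plan alone has real force. Analysing eligible patients is a familiar phase II convention. Eligibility here rests almost wholly on baseline facts, and 14.2 already bars the most dangerous outcome-related exclusions from supporting efficacy claims. The calculated effects are small and rest on assumed losses. All of that stands, and it limits the size of the point. It does not supply the missing PFS start date or analysis set.

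A reader might infer more than the text supports:

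- **That untreated patients may be dropped from PFS and OS under the exception.** The exception belongs to the main response-rate analysis only. OS loses never-treated patients through its time origin instead.
- **That 14.2 certainly fixes an eligible-only set for PFS.** It may not, given its heading. But if it does not, the primary endpoint has no stated set, and the same sentence of repair is needed.
- **That the false-positive rate is inflated.** This would need patients with poor prognosis to be lost mainly from one arm. Nothing in the documents shows or predicts that.
- **That many PFS events would fall before first dose.** Repeat imaging is every 8 weeks under 5.4, and none is scheduled between randomisation and first dose. In a short gap, mainly deaths would be recorded.
- **That departing from the cited phase 3 temsirolimus trial is itself an error.** Section 3.2.3 reports that "The ITT population for this interim analysis included 626 patients" and times OS from randomisation. But the test here is between concurrent arms, and another trial's convention does not bind it.

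**Conclusion.** The point holds as a cheap improvement. The text shows an eligible-patient basis for conclusions, an open exception for the response rate, an OS origin later than randomisation, and a primary endpoint with no start date and no set of its own.

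The gain is protection of the randomised comparison plus about 1 to 3 points of power. That range assumes 2 to 4 patients per arm lost at random, exponential times and nearly complete events. Type I error is essentially unchanged under those losses. The power matters a little because the design has almost no reserve once the futility look is counted. Bias is possible only if losses are both related to prognosis and unequal between arms, and the documents give no sign of that.

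**What to change.** In 13.0 and 14.2, state that:

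- PFS, OS and response are analysed in all randomised patients, in the arm assigned.
- PFS and OS are timed from the date of randomisation.
- Patients with no post-baseline scan count as non-responders.
- Eligible-only and treated-only analyses are sensitivity analyses.
- Safety uses patients who received at least one dose.

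Delete the untreated exception and the eligible-only sentence from 14.2. Add a line for never-treated patients: follow them for survival by the phone, e-mail or record-review method in 5.7. For PFS, count death as an event; otherwise censor at the last tumour assessment, or at randomisation if there is none. This line is needed because 5.7 starts survival follow-up at removal from study therapy, and 5.4 places repeat scans within treatment.

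The cost is some wording, a little follow-up work and a recorded randomisation date for each patient (assumed to be held by the randomisation program). The reported response rate may be slightly lower, as in the 8.9% against 9.3% illustration. One limit remains: a never-treated patient who is alive and unscanned adds nothing to PFS, so for such patients the gain is in OS and response. The sentence in 14.2 that censors unrelated deaths is a separate matter.

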10.4 Confirmatory Measurement/Duration of Response

10.4.1 Duration of overall response

The duration of overall response is measured from the time measurement criteria are met for CR or PR (whichever is first recorded) until the first date that recurrent or progressive disease is objectively documented (taking as reference for progressive disease the smallest measurements recorded since the treatment started).

The duration of overall CR is measured from the time measurement criteria are first met for CR until the first date that recurrent disease is objectively documented.

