 - Important medical events as defined above, may also be considered serious adverse events. Any important medical event can and should be reported as an SAE if deemed appropriate by the Principal Investigator. All events occurring during the conduct of a protocol and meeting the definition of a SAE must be reported to the IRB in accordance with the timeframes and procedures outlined in “The University of Texas M. D. Anderson Cancer Center Institutional Review Board (IRB) Policy for Investigators on Reporting Unanticipated Adverse Events for Drugs and Devices”. For this protocol adverse events will be captured according to the Recommended Adverse Event Recording Guideline for Phase II protocols (below).

Recommended Adverse Event Recording Guidelines					
Attribution	Grade 1	Grade 2	Grade 3	Grade 4	Grade 5
Unrelated	Phase I	Phase I	Phase I Phase II	Phase I Phase II Phase III	Phase I Phase II Phase III
Unlikely	Phase I	Phase I	Phase I Phase II	Phase I Phase II	Phase I Phase II

				Phase III	Phase III
Possible	Phase I	Phase I	Phase I	Phase I	Phase I
	Phase II	Phase II	Phase II	Phase II	Phase II
		Phase III	Phase III	Phase III	Phase III
Probable	Phase I	Phase I	Phase I	Phase I	Phase I
	Phase II	Phase II	Phase II	Phase II	Phase II
		Phase III	Phase III	Phase III	Phase III
Definitive	Phase I	Phase I	Phase I	Phase I	Phase I
	Phase II	Phase II	Phase II	Phase II	Phase II
		Phase III	Phase III	Phase III	Phase III

The Investigator or physician designee is responsible for verifying and providing source documentation for all adverse events and assigning the attribution for each event for all subjects enrolled on the trial

- **Serious adverse events will be captured from the time of the first protocol-specific intervention, until 30 days after the last study treatment/intervention, unless the participant withdraws consent. Serious adverse events must be followed until clinical recovery is complete and laboratory tests have returned to baseline, progression of the event has stabilized, or there has been acceptable resolution of the event.**
- **Additionally, any serious adverse events that occur after the 30 day time period that are related to the study treatment must be reported in accordance with the IRB policy. This may include the development of a secondary malignancy.**

Reporting to FDA:

- SAE's will be reported per regulatory (local and federal) guidelines.

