15.3 Accuracy of Data Collection

At an appropriate time, an independent panel of hired radiologists will review all imaging studies to assess progressive disease and response in each patient, but the principal investigator at each institution will be responsible for decision regarding the treatment phases of each patient on this trial.

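### Section 14.2 censors on-therapy deaths of unrelated cause without naming an endpoint, which contradicts the PFS hypothesis and the OS definition; no PFS rule overrides it

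*Combined protocol and SAP*

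**What the plan says.** The last sentence of section 14.2 (Evaluation of response) reads: "Patients who die of unrelated cause during therapy or are lost to follow-up shall be censored". It is worded as mandatory, names no endpoint, does not define an unrelated cause and does not say who judges it.

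Section 13.0 bears on the same deaths in two places:

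- **PFS (primary).** The clinical hypothesis is "whether patients receiving the experimental therapy have a lower hazard of progression or death relative to patients receiving the control therapy". No cause of death is excluded.
- **OS (secondary).** "Overall survival is calculated from day of therapy initiation to the date of death", and the only censoring rule is "Patients who are lost to follow-up will be censored at date of last contact".

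Section 10.4.1 runs duration of response "until the first date that recurrent or progressive disease is objectively documented", and section 10.4.2 likewise ends duration of stable disease at progression. Section 1.0 lists TTP as a secondary objective, but the documents give it no event or censoring rule. They also contain no PFS definition with start date, events and censoring.

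**The concern.** Censoring deaths without progression suits endpoints that end only at documented progression: TTP, duration of response and duration of stable disease. It does not suit PFS or OS as section 13.0 describes them. Because section 14.2 names no endpoint and PFS has no censoring rule of its own, two analysts could follow this document and count different primary events.

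Applied to PFS or OS, the rule would remove on-therapy deaths as events and raise the Kaplan-Meier curves. For PFS, it would also make the event count, including the 42 events that trigger the futility look, depend on attributing cause of death. The plan provides no independent check on that attribution: under section 15.3 "an independent panel of hired radiologists will review all imaging studies to assess progressive disease and response in each patient", which does not cover cause of death. The people attributing cause would probably know the treatment. This is inferred, because one arm is oral, the other is intravenous, and no masking is described.

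The undefined term widens the problem. The only place the documents use Unrelated as a category is the adverse event table in section 11.0, where the investigator or designee is responsible for "assigning the attribution for each event for all subjects enrolled on the trial". If that meaning (unrelated to study treatment) were carried over, even a cancer death without documented progression could be censored.

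**Working it through.** **The rules side by side**

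| Endpoint | What its own text says about death | Does the 14.2 rule fit? |
|---|---|---|
| PFS | Part of the hypothesis, any cause (13.0); no censoring rule | No |
| OS | The event, any cause; censored only for loss to follow-up (13.0) | No |
| TTP | No definition | Yes |
| Duration of response | Ends at documented recurrence or progression (10.4.1) | Yes |
| Duration of stable disease | Ends at progression (10.4.2) | Yes |
| Response rate | A proportion, not censored | Not applicable |

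The loss-to-follow-up half of the 14.2 sentence agrees with the OS rule. Only the unrelated-death half conflicts.

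**Reproducing the plan's design**

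Inputs from section 13.0: medians 3.8 and 6.1 months, one-sided alpha 0.10, power 0.80, 1:1 allocation, 90 patients, futility look at 42 events with stopping if p > 0.4798. The final event count is not stated.

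- HR = 3.8/6.1 = 0.623; ln HR = −0.473; (1.2816 + 0.8416)² = 4.508.
- Freedman: [(1 + 0.623)/(1 − 0.623)]² × 4.508 = 83.5 events.
- Schoenfeld: 4 × 4.508/0.473² = 80.5 events.

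The 42-event look is half of 84, so 84 final events is the natural inference. Power and type I error treat the interim and final Z statistics as bivariate normal, with mean −ln(HR) × √d/2 at d events and correlation √(42/d_final). The interim p-value is taken as one-sided and the final critical value is 1.2816. At 84 events this gives type I error 0.094 and power 0.794, which matches the planned 0.80 closely.

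**Applying the 14.2 rule to PFS**

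With exponential times, censoring a share f of an arm's PFS events multiplies that arm's counted hazard by (1 − f). The apparent HR is then the true HR × (1 − f_paz)/(1 − f_tem), and the final event count is 84 × [1 − (f_tem + f_paz)/2]. The look stays at 42 counted events. The shares are assumptions.

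| f_tem | f_paz | Final events | HR shown when true HR = 1 | Type I error | HR shown when true HR = 0.623 | Power |
|---|---|---|---|---|---|---|
| 0 | 0 | 84 | 1.000 | 0.094 | 0.623 | 0.794 |
| 5% | 5% | 79.8 | 1.000 | 0.095 | 0.623 | 0.782 |
| 10% | 10% | 75.6 | 1.000 | 0.096 | 0.623 | 0.769 |
| 5% | 15% | 75.6 | 0.85/0.95 = 0.895 | 0.205 | 0.557 | not meaningful* |
| 15% | 5% | 75.6 | 0.95/0.85 = 1.118 | 0.037 | 0.696 | 0.601 |

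*The rejection rate rises here only because the HR is biased toward benefit.

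Worked case, 5%/15% under no effect: −ln(0.895) = 0.111. The final mean is 0.111 × √75.6/2 = 0.484, so without the look the error is P(Z > 1.2816 − 0.484) = 0.212. With the look it is 0.205.

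Timing of the look: 42 counted events correspond to 42/0.95 = 44.2 any-cause events at a 5% share and 42/0.90 = 46.7 at 10%.

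Medians: a 10% share in both arms would lift the apparent medians from 3.8 and 6.1 to 3.8/0.90 = 4.2 and 6.1/0.90 = 6.8 months.

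A simulation of 20,000 log-rank trials (90 patients, assumed uniform accrual over 30 months) agreed. Type I error was 0.095 with no such censoring, and 0.203 and 0.038 for the two unequal cases. Power was 0.784, 0.770 and 0.759 at equal shares of 0, 5% and 10%.

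No OS figure is given, because the rule reaches only deaths during therapy and the documents do not state what fraction of deaths those are.

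**The case against.** The best case for the plan is that section 13.0 is the endpoint-specific text and already settles the matter. The sentence in 14.2 sits under a response heading, so it may have been meant for TTP or duration of response. The same section allows exclusions for early death from other reasons only in sub-analyses that cannot support efficacy conclusions, which leans against special treatment of such deaths in the main analysis. OS has its own censoring rule. Unrelated most naturally means unrelated to the disease, and the adverse event table is not cited in 14.2.

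Much of this is fair. The defect is an unresolved contradiction, not proof that PFS deaths will be censored. OS is the weaker half, and the reading taken from the adverse event table is only a possibility. But a response rate is not censored, so the heading does not explain the sentence. A limit on excluding patients is also not a rule on censoring them. No text confines the sentence to TTP, and PFS has no definition to set against it.

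The size is also open to challenge. The striking figures need a threefold difference between arms, roughly 6 against 2 deaths among 42 events per arm. At 2% against 5%, the same method gives type I error 0.12 if more are censored on pazopanib, or 0.07 if more are censored on temsirolimus, with power 0.74 in the latter case. The model also lets final events fall while holding the look at 42 counted events, which implies a calendar cut-off the plan does not state. The figures are illustrations. The finding rests on the text.

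**Conclusion.** The concern holds. As written, section 14.2 contradicts the primary hypothesis and the OS definition, and the plan leaves open what counts as a primary-endpoint event in a 90-patient trial. This should be fixed before analysis.

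The consequence depends on how many deaths are affected and how they split by arm. Equal shares of 5% to 10% cost about 1 to 2.5 points of power and leave the HR unbiased. Unequal shares of 5% and 15% either roughly double the one-sided type I error or cut power to 0.60, and the direction cannot be predicted. These results assume exponential times, an inferred total of 84 events and hypothetical shares. The contradiction itself depends on none of these.

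**What to change.** Replace the last sentence of section 14.2 with:

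*For PFS and OS, death from any cause is an event. For TTP, duration of response and duration of stable disease, deaths without documented progression are censored at the last tumour assessment. Patients lost to follow-up are censored at the last tumour assessment (PFS, TTP, duration of response, duration of stable disease) or at last contact (OS).*

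This agrees with sections 10.4.1, 10.4.2 and 13.0 and keeps death-censoring where it fits. It removes cause-of-death attribution from the primary event count and leaves power at about 80%. Censoring at the last tumour assessment is a convention added here; the documents do not state one. The cost is a short wording change, with no new data.

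The PFS start date and the rule for patients alive and progression-free at data cut-off are also missing. That is a separate gap, and the same amendment could close it.
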